There have not been any serious consequences associated with TRYP administration. TRYP is sold over the counter (FDA Dietary Supplement Health and Education Act of 1994 (DSHEA)) and has been available for over 50 years. TRYP is mostly acquired through dietary consumption, but increasing tryptophan is possible with using pure TRYP as in this study which is intended to produce kynurene. TRYP loading has been widely used in clinical research. A recent review covers 43 studies that assessed TRYP loading. The dosing in these studies varied, with many studies using aggressive loading doses (>10 g/day) (126-130), while others have used dosing of 5-10 grams (131-136). We propose to use a dose of 6 grams. This literature review does not demonstrate any significant side effects other than some minor transient effects on cognition, mood and sleep. On the contrary, there have also been improvements observed in memory and attention, and worsening of memory, attention, executive dysfunction and psychomotor speed generally occurred only at very high concentrations of TRYP (118). Similar is true to mood; improvements have been seen in anger, depression, vigor and alertness but high concentrations of TRYP have shown minor worsening in these domains in a few studies (118). Abnormal sleep behaviors have been improved in many studies; however, sleepiness is a reported side effect (118). Occasional side effects have been reported at higher TRYP doses (generally >6 grams daily), which include tremor, nausea, and dizziness (137). Mild dyspepsia and diaphoresis have occurred in people ingesting TRYP. The dose used in this study is lower than that used in most published studies. By giving the water and TRYP mixture slowly we will mitigate dyspeptic reactions. A very recent study (138) reported on the side effects of up to 5 gram/day of TRYP in healthy volunteers and found no changes in laboratory measures, food intake, body weight or mood side effects. In schizophrenia, we anticipate only mild, transient effects on cognition. In 1988 and 1989, there was an outbreak of eosinophilia-myalgia syndrome (EMS) that was traced to a single

manufacturer in Canada, leading to a ban in the US for 12 years; however, this is no longer considered a risk, and the ban was lifted in the US in 2001 (139).

One potential serious side effect is the serotonin syndrome, which could occur when TRYP is administered in combination with other serotonergic agents. The occurrence of the serotonin syndrome with TRYP is rare and generally only occurs after routine use of TRYP. The serotonin syndrome includes the following symptoms: delirium, myoclonus, hyperthermia and coma. We will include these items in the SEC as potential side effects to ensure our ability to detect their occurrence.

In summary, side effects with TRYP are mild, even in studies that have used higher doses for longer periods of time than will be done in the current study (118).

Adequacy of Protection Against Risks

Informed consent:

Schizophrenia-Related Disorders: A partial HIPPA waiver will be obtained to permit the identification of potential participants through chart review. In addition, participants will be referred by the person's treatment team for consideration of study participation. No potential SRD participant will be approached for recruitment without approval of a primary clinician, who will determine suitability of the person for the protocol. A chart review will be completed for all potential SRD participants to reduce the likelihood that they will be found ineligible after participating in more extensive assessment. The study recruiter will verify with the primary clinician that a potential participant is sufficiently stable to consider participation and has capacity to provide consent. This is done prior to the study recruiter approaching a potential participant. The study recruiter will be introduced to the person and provide a brief overview of the project. Research staff members are trained to recognize symptoms of severe mental illness and cognitive impairment that could undermine an individual's ability to provide informed consent.

All Participants: Interested people will be provided study information and an informed consent form that contains all pertinent details of participation and includes the following: a brief explanation of the purpose of the research and a brief explanation of the requirements of the participant, including: a) willingness to be randomly assigned to either intervention, b) completing a series of interviews about symptoms, c) completing assessment tasks, and d) being available for follow-up assessments. The consent form will include an explanation of the risks and benefits of participation; assurances of confidentiality; and an explanation that participation is entirely voluntary, the decision to participate will in no way influence or restrict services at participating sites, and the participant is free to withdraw at any time with no negative consequences. Potential participants will be informed that the drug used in this study is not known to be effective for any indication under investigation. As some potential participants will have poor reading skills, the consent form will be read aloud to all participants in tandem with their own silent reading of the document. The individual securing consent will review any points about which the participant is unclear, and the participant will be invited to ask questions as needed.

Our research staff is carefully trained in strategies for interacting with people with severe mental illness, including speaking slowly and clearly, stopping to summarize frequently, and providing time for questions. They are all supervised by senior staff members. All participants who express willingness to provide consent will be queried about the consent form in order to ensure that they have adequate understanding of the study requirements. This questioning is performed systematically, and research staff members document that this review has been completed. After reading the consent, and before obtaining a signature, a brief questionnaire is

administered to verify that the participant is competent to provide consent and has demonstrated comprehension of the consent document. This questionnaire is attached to the informed consent form and is completed immediately after explaining the informed consent form and before obtaining the participant's signature on the form. If the participant does not understand the consent form, the recruiter will try to explain points of confusion, and administer the questionnaire again. Those failing to answer the questions adequately will not be recruited into the study. The recruiter will also make a clinical judgment and not recruit participants who appear unable to grasp key aspects of the procedure. This approach, which requires a proactive demonstration on the part of the participant that they understand what is being requested, has been used extensively at the MPRC. Included participants must also be judged competent to consent by the Evaluation to Sign Consent (ESC) questionnaire, and provide voluntary informed consent. Per University of Maryland School of Medicine IRB regulations, a copy of the signed consent form is given to the participant, a copy is placed in the person's medical record, and the original is kept in the laboratory. Research assistants obtaining informed consent will be experienced clinicians. They will receive detailed and standardized training as to how to obtain informed consent from people with serious mental illnesses. They will be observed obtaining informed consent from a study participant by senior staff prior to being allowed to recruit on their own.

Protections Against Risk:

We will make every attempt to minimize all study-related risks. Sexually active women of childbearing age will agree to the use of medically approved birth control, which includes condoms, oral contraceptives, diaphragms, or intrauterine device for 2 weeks after the study. Pregnant and lactating females will be excluded. We will test for pregnancy at each visit. In addition, the Brief Stay Unit (BSU) is a psychiatric and medical unit with an ACLS-certified nurse and physician. The BSU is stocked with an emergency medication supply and crash cart and has direct line to the adjacent hospital for emergency support. All BSU staff are trained in behavioral and medical emergencies. Because we hypothesize that the kynurenone pathway dysregulation may be present in schizophrenia and KYNA level increases may be associated with the pathophysiology of the illness, we anticipate slight worsening in neurocognition in the schizophrenia group. However we do not anticipate worsening in clinical symptoms. We will be carefully monitoring for side effects and distress in a well-staffed medical unit with psychiatric and medical coverage. We have a full backup emergency plan and available medications for medical and psychiatric emergencies. In order to provide objective criteria for distress and symptom worsening and study discontinuation, we have developed the following criteria:

- Participants will be withdrawn from any remaining study assessments if at any time there is significant distress reported by the schizophrenia patient or control.
- To be objective in psychiatric symptoms, we will apply a modified battery of psychiatric assessments after TRYPT administration and prior to imaging. This modified assessment allows us to specifically monitor psychotic symptoms, hostile behavior or suicidality.
- Thus, we will look out for an increase in 3 or more points from the premedication BPRS in positive symptoms, somatic concern, or hostility on the BPRS, a score of a 3 or more on the suicidality item on the Calgary Depression Scale (item 8), or a two or more point increase on the CGI. If a participant scores ≥ 6 and this is at least a two point increase from baseline, the study procedures will be discontinued.
- At any time, however, a participant can be discontinued from the study.

Throughout the challenge, we will closely monitor for side effects, tolerability and any signs or symptoms of serotonin syndrome. Heart rate, blood pressure, temperature, diaphoresis, and

muscle twitching will be monitored continually. With regards to imaging, prior to entry to the study, participants are carefully screened for medical illness and to ensure that they will be safe in the MR scanner. All participants are screened for contra-indications for magnetic resonance, namely severe claustrophobia, pregnancy, cardiac pacemaker, orthodontics, or other non-MR compatible ferromagnetic implant. In addition, access to the scan room is strictly controlled to ensure that no ferromagnetic materials are introduced. The scanner to be used in the study is FDA approved and operates under radiofrequency power monitoring software at all times. All scan procedures at magnetic field strengths of 1.5T and 3T are FDA approved and are not classified as investigational devices. Some participants may become claustrophobic, bored or restless during the testing. The participants have the option of terminating the testing at any time without penalty if they so choose. The risks of psychological discomfort will be minimized by encouraging participants to let the examiner know if they are feeling any discomfort, and by continuous monitoring by experienced operators for participant fatigue, inattention, or annoyance. Scanning will be halted if the participant so requests, or if the examiner feels that the participant is becoming uncomfortable. The participant will be encouraged to report any adverse symptoms during the MRI. The MRI can be stopped by the participant either by verbalizing the request to stop (which can be heard through the microphone in the MRI) or by pushing a “panic button” provided to him/her. A potential concern with MRI studies is so-called radio-frequency heating due to radiofrequency power deposition in the participant. The FDA has set strict and very conservative guidelines to guard against this risk. Such power deposition increases with the square of the magnetic field strength. To be 100% sure of compliance with the FDA guidelines, power deposition is monitored continuously by the software of the manufacturers, and scans are not possible if the power deposition exceeds guidelines.

Confidentiality

All records of the research will be kept in locked files with subjects identified by code only. A separate file will hold the code key. Subjects will not be personally identified in any publications or reports of the study. All biological specimens collected for research purposes will be identified at the laboratory by code only. Whenever possible, existing clinical laboratory data will be used as a source of information for the study, which will minimize testing done on subjects. Any data used will be recopied to research files with the subject identified by code only. Computerized records of data are kept in password-protected computers in locked rooms. Appropriate firewalls and protections of computerized data are maintained to ensure that entry by those other than research personnel is not possible.

Potential Benefits of the Proposed Research to the Participants and Others There are few potential benefits to participating in the study. Participants will have a series of medical and laboratory workup prior to study start that may provide new or helpful information on their physical and mental health. Mild and transient changes in neurocognition are possible or even expected. We feel the importance of the knowledge gained outweighs the risks of the study.

Importance of the Knowledge to be Gained:

We will be able to examine, for the first time, the connection between the kynurene pathway, cognitive function and neuroimaging in people with schizophrenia. In addition, we will examine the role of stress hormones and immune function in the control of kynurene pathway metabolism. This important information could be the first clinical study to link this pathway to symptoms and outcomes of people with schizophrenia.

Data and Safety Monitoring Plan:

A Data Safety Monitoring Board (DSMB) is already established for monitoring studies at the MPRC and will be used for this study. The DSMB is comprised of two psychiatrists, a pharmacist, a statistician, and a community representative. The psychiatrist will be an expert in the clinical treatment of people with schizophrenia. The DSMB will be charged with the following responsibilities: 1) to establish a regular meeting schedule; 2) to review the protocol; 3) to review the consent form; 4) to monitor the occurrence of side effects/adverse events, and serious adverse events throughout the course of the study; and 5) to review with investigators, the study data management system; and 6) to establish stop rules for the study as a whole. The DSMB will review prior to study enrollment and then receive annual side effect/adverse event updates. In addition, all serious adverse events (SAEs) will be reported to the DSMB, PIs, and the University of Maryland School of Medicine IRB. The PI will receive all SAE reports within 24 hours of their occurrence. If the incidence of any side effect/adverse event is 25% or more or any SAE occurs in excess in either treatment group, the DSMB will notify the PI. The PI and the DSMB will determine whether possible protocol modifications are required to minimize the further occurrence of such events. Unexpected adverse events will be reported in accord with NIH and Federal requirements. Non-serious and expected adverse events will be reported annually to the IRBs. The PI is required to attend the DSMB meeting annually and is asked to give a review of the past year with a particular emphasis on safety, side effects, and enrollment. The data would remain blinded unless risks to participants justify unblinding. To safeguard confidentiality, data are presented in aggregate or are identified only by an ID number.

6. Clinical Trials.Gov Requirements:

The study will be registered on ClinicalTrials.gov prior to the enrollment of any participants.

Literature Cited:

1. Schwarcz R, et al (2001) Increased cortical kynureneate content in schizophrenia. *Biol Psychiatry* 50:521-530.

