Assessment Schedule: The clinical assessments will be administered prior to administration of the study medication, immediately prior to the MRI scan, upon completion of the MRI scan, and at the follow-up safety assessment, which will be conducted 75 min after the completion of the MRI scanning. The cognitive assessments will be conducted prior to the administration of the study medication and after the MRI scanning is completed and the participant has had lunch. The laboratory assessments will be collected at pre-TRYP challenge baseline, and 30 min, 60 min and 90 min post ingestion. The final laboratory assessment will be collected at the time of the second administration of the cognitive battery. The safety assessments will be administered

prior to administration of the study medication, every 30 min after medication administration, upon completion of the MRI scan, and at the follow-up safety assessment.

Table 1. Assessment Schedule.

	Study Lead In (up to 2 weeks)	Challenge Visit: Estimated Time of Assessment	Challenge Visit: Actual Time of Assessment	Initials
Informed Consent, ESC	X			
SCID and diagnostic interview, MRI screening	X			
Medical Screening Medical Hx, physical exam, blood draw, urinalysis, toxicology screen, pregnancy test (females), EKG, medication use screening, caffeine use screening, Birth Control Selection (females)	X			
Clinical Stability Determination (schizophrenia group only seen on two visits, healthy controls one visit) 2 unchanged CGIs	X			
Mock scanning session	X			
Scheduling of 2 challenge visits and NPO order for 12 hours in advance of admission on challenge study days	X			
Participant Admission/BSU Arrival Review of Study Procedures and retrospective recall of food intake (past 12 hours). Collect personal items not safe during MRI testing.		7:30 am		
Urine pregnancy (females), expired CO, urine toxicology and blood alcohol testing, MRI screening		7:45 am		
Insertion of indwelling IV line, fluids, period of relaxation		8:00 am		
Laboratory Assessments (1): cortisol, ACTH, kynurenine, KYNA, 3-HK, cytokines		8:15 am		
Cognitive Measures (1): HVLT-R, BACS Symbol Coding, BVMT, CPT-IP, WMS®-		8:30 am		

III, LNS				
Vital signs, SEC, SSS Clinical Assessments (1): BPRS, SANS, CDS, CGI		9:15 am		
Oral Administration of Medication (Tryptophan 6 gram/ Placebo)		10:00 am		
Protein Free Snack		10:15		
Vital signs, SEC, SSS Laboratory Assessments (2)		10:30		
Vital signs, SEC, SSS Laboratory Assessments (3)		11:00 am		

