Clinical Assessments (2; modified version)		11:15 am		
Vital signs, SEC, SSS Laboratory Assessments (4)		11:30 am		
Arrive at Imaging Center		11:45 am		
Neuroimaging Studies		12:00 pm		
Arrive Back at BSU Vitals, SEC, SSS		1:40 pm		
Lunch		1:45 pm		
Cognitive Measures (2) Laboratory Assessments (5)		2:00 pm		
Clinical Assessments (3; modified version) Vital signs, SEC, SSS		2:30 pm		
Participant discharged. If participant has not returned to pre-		2:45 pm		

tryptophan challenge baseline, they will be reassessed every 30 minutes until ready

Neuroimaging Procedures: All MRI data will be acquired using a 3-T Siemens Trio scanner equipped with a 32 channel head coil at the University of Maryland Center for Brain Imaging Research (CBIR), located at the Maryland Psychiatric Research Center. A T1-weighted structural image (MP-RAGE: 1 mm isotropic voxels, 256 X 256 mm FOV, TR/TE/TI = 1900/3.45/900ms) will be acquired for spectroscopic voxel prescription and anatomical reference.

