Double-Blind Challenge Phase: The Double-Blind Challenge Phase will utilize a placebo-controlled, cross-over design. Participants who continue to fulfill entry criteria will be entered into the Double-blind Challenge Phase. There will be two Challenge Phase visits. On the day of each visit, the participants will arrive at the Brief Stay Unit (BSU) at 7:30AM; all participants will have fasted since midnight. At the BSU, an indwelling I.V. will be inserted for the repeated laboratory assessments and the initial clinical, cognitive, laboratory, and safety assessments (including urine pregnancy test for female participants) will be completed. Upon completion of the initial assessments, participants will receive the challenge medication. Participants will be randomly assigned to receive TRYP (6 grams) or placebo. They will receive the other study medication on the second visit (i.e., placebo or TRYP). The 6 gram dose was chosen based on previous work showing cognitive effects to be associated with doses above 5 grams (118) and our pilot work, in which we have demonstrated that, in ten healthy controls TRYP (6 grams) produces a robust increase in kynurenone. TRYP and placebo will be administered in oral slurry. A non-blind pharmacist will dispense all study medications. The blind will be broken only if a medical emergency requires this information. If this occurs, the participant will be withdrawn from the study. Two hours after ingestion of TRYP or placebo, participants will be transferred to the CBIR, which is in a building adjacent to the BSU, where they will undergo the following MRI assessments: 1) spectroscopy for the assessment of glutamate, 2) fMRI resting scan; and 3) fMRI during relational and item memory tasks. We chose to begin scanning 120 min after study medication ingestion, because our preliminary data suggests that serum kynurenone initially becomes elevated 30 min after TRYP ingestion, but continues to increase over the next three hours; we wanted to ensure sufficient time for kynurenone to cross the BBB and be converted to KYNA. Kynurenone levels will remain elevated for at least 3.5 hours, which is sufficient time to complete the MRI assessments and post-imaging cognitive assessments. The cognitive assessments will be conducted prior to the administration of the study medication and after the MRI scanning is completed. The post-baseline clinical, laboratory, and safety assessments will be conducted as described above.

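### Minor: no contact is scheduled after visit 2, so the half who take TRYP last are never systematically asked about side effects that start after discharge, about 4.75 h after the dose.

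*Combined protocol and SAP*

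**What the plan says.** The Assessment Schedule text places safety assessments before the dose and then "every 30 min after medication administration, upon completion of the MRI scan, and at the follow-up safety assessment". The same paragraph fixes the last of these: "the follow-up safety assessment, which will be conducted 75 min after the completion of the MRI scanning".

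In Table 1 the pre-dose row at 9:15 am reads "Vital signs, SEC, SSS Clinical Assessments (1): BPRS, SANS, CDS, CGI", the dose is at 10:00 am, and the last row with an SEC, at 2:30 pm, reads "Clinical Assessments (3; modified version) Vital signs, SEC, SSS". Discharge is estimated at 2:45 pm. For anyone not back to the pre-challenge state, "they will be reassessed every 30 minutes until ready".

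The Double-Blind Challenge Phase has two visits in cross-over: "They will receive the other study medication on the second visit". Randomization and Blinding balances the order within blocks. No call or visit is listed after the second challenge day.

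The Data and Safety Monitoring Plan has a notice rule, "If the incidence of any side effect/adverse event is 25% or more", on which the DSMB informs the PI. It also has the board "receive annual side effect/adverse event updates".

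**The concern.** The label of the last safety assessment suggests a later contact, but it is an in-visit item. The half-hourly reassessment extends observation only for people who still have effects before they leave, so it cannot reach an effect that begins at home.

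The protocol gives some reason to look later. Potential Risks to Human Subjects lists transient effects on mood and sleep, and sleepiness. A visit that ends mid-afternoon cannot observe that night's sleep. The Challenge Phase section says kynurenine stays raised for at least 3.5 hours and gives no upper limit. Serotonin syndrome is described as rare but possible with other serotonergic agents.

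At stake is the completeness of the side-effect record for a single 6 g dose, and what the 25% rule counts. The rule's wording covers any side effect, while systematic questioning stops at discharge.

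**Working it through.** **Clock times (Table 1 estimates)**
- Dose 10:00 am to last SEC 2:30 pm = 4.5 h.
- Dose 10:00 am to discharge 2:45 pm = 4.75 h.
- By the text rule (scan end + 75 min, scan start 12:00 pm): a 75-min session gives 2:30 pm (4.5 h), 90 min gives 2:45 pm (4.75 h), and 100 min gives 2:55 pm (about 4.9 h). All are on the same day, at or near discharge.

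**Who is not asked again**
- Recruitment: 50 + 50 = 100 enrolled. With 10% attrition, 50 × 0.9 = 45 completers per group, which reproduces the plan's figure and gives 90 in all.
- With balanced order, TRYP-last = 100/2 = 50 enrolled, or 90/2 = 45 completers.
- The TRYP-first half has one later SEC, at 9:15 am on visit 2, for those who return. Its recall period is not stated, nor is the interval between visits. Anyone who drops out after a TRYP visit 1 is also not asked again.

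**Illustration of the 25% rule (assumed rates only)**

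The documents give neither the incidence p of a side effect on TRYP nor the share L that starts after discharge. Assume one side effect and yearly cumulative looks at 18 participants a year: n = 18, 36, 54, 72, 90. The rule needs a count of at least 0.25n, so the thresholds are 5, 9, 14, 18 and 23. With no late event captured, each look adds a Binomial(18, p(1 − L)) count. The exact chance that the rule fires at any look is:

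| p | L = 0 | L = 10% | L = 20% |
|---|---|---|---|
| 10% | 0.032 | 0.021 | 0.012 |
| 15% | 0.161 | 0.107 | 0.067 |
| 25% | 0.762 | 0.609 | 0.439 |
| 30% | 0.944 | 0.856 | 0.704 |
| 40% | >0.999 | 0.996 | 0.974 |

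At p = 30% and L = 50% it is 0.161. If spontaneous or clinician reports catch half of the late events at p = 30%, it is 0.908, 0.856 and 0.609 for L = 10%, 20% and 50%.

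At p = 30% and L = 20%, perfect look-back by the TRYP-first half (9 per look at 0.30, 9 at 0.24) gives 0.856. Adding calls that catch 80% of late events in the TRYP-last half (9 at 0.30, 9 at 0.30 × (1 − 0.2 × 0.2) = 0.288) gives 0.931.

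The largest drops occur when p is close to the 25% trigger. At 10% the rule seldom fires in any case; at 40% it nearly always fires with up to 20% late.

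**The case against.** The strongest reply is that this asks for more follow-up than a single oral dose needs. Potential Risks to Human Subjects cites a review of 43 loading studies with only minor transient effects, calls side effects mild even at higher doses for longer, and reports few in ten healthy controls at 6 g. Participants are observed for nearly five hours, monitored continually for signs of serotonin syndrome, and kept until back to baseline. The 25% rule only gives notice to the PI, and the board sees the counts each year whether or not the threshold is crossed. Serious adverse events have their own 24-hour reporting route. All of this stands, and it is why the point is minor.

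The illustration is also open to attack, fairly. Its rates are assumed, the clearest losses lie near the trigger, and it follows one side effect while the SEC rates 32. With two independent side effects at 30% and 20% late, the rule would fire on at least one with probability 1 − (1 − 0.704)² = 0.91. No weight should rest on any single cell.

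What does not stand is that the gap is already covered. The board's remit and the reporting rules act on events once known; they schedule no question to participants. Informed Consent mentions availability for later assessments, but the schedule lists none after discharge. The consent form is not in the copy reviewed, so any instruction there to report later problems cannot be judged either way.

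**Conclusion.** The gap is real and small. About 45 to 50 TRYP-last participants have no scheduled side-effect question after discharge; later events would be learned of only by spontaneous or clinician report. TRYP-first participants have at most an SEC at visit 2 that may or may not reach back. This follows from the schedule and needs no assumed rate. How many events are lost is unknown.

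A reader might infer more than the documents support:
- That nobody is asked anything after the first challenge day. Everyone who returns has the visit-2 pre-dose SEC.
- That monitoring for serotonin syndrome is inadequate. In-visit monitoring is thorough; only the time after discharge is uncovered.
- That the 25% rule is defeated, or that the schedule contradicts the board's remit. The rule's loss depends on rates the documents do not give, and the monitoring plan sets no observation window per participant.
- That the results are biased. No efficacy aim or analysis is affected, and the in-visit window is the same on TRYP and placebo days.

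**What to change.** 1. Add one short scripted SEC call by existing staff the day after each challenge visit, identical for TRYP and placebo, as one line in Table 1.
2. At visit 2, add a separate question about the time since the last visit. Leave the pre-dose SEC as a current-state measure. It is part of the same-day baseline against which discharge readiness is judged, and mixing in interval complaints could mask new effects that day.
3. Report post-discharge events to the DSMB by coded condition, separately from in-visit counts, so that the data stay blinded.

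If calls are not adopted, keep the separate look-back question and state that the systematic counts behind the 25% rule run only to discharge.

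Cost: 2 × 100 = 200 short calls in all, or 2 × 18 = 36 a year, and one added question. Some calls will be missed. More minor background complaints will be recorded on both days, which could add some 25% notices because that threshold is not a comparison with placebo; separate tabulation keeps this visible.
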